Subsequent recruitment. Subsequent PHAs (Waves 2-4) will be drawn from workshop attendees (who do not have to agree to be PHAs), and their numbers will be supplemented if needed using Wave 1 recruitment procedures. At the end of a workshop (or, for IA participants, after viewing the online materials), study staff will invite all participants to become PHAs and to reach out to their network members to help them prevent HIV infection. PHAs will invite network members to participate in the activity (GE or IA) they, themselves, participated in (and will inform them that brief assessments are included). We will repeat this process three more times, for a total of four recruitment “waves” (see Table below). We expect that the initial PHAs (n=16, Wave 1) will refer 28 workshop attendees. Of these 28, we expect at least 50% will agree to be PHAs (Wave 2). These 14 will average two referrals (n=28) who are eligible and participate. We expect half of participants to agree to be PHAs (Wave 3), through a total of four waves. If we fail to enroll 14 new PHAs from the pool of attendees, we will add new recruits, as for the initial seeds. We expect each wave will take approximately two months. To attain a target **98 100** participants attending and completing Waves 2 through 4, we anticipate that we may need to enroll up to 120 women.

Peer-driven recruitment waves and follow-up N = 100 <del>98</del> 100	Wave 1 (seeds)	Wave 2	Wave 3	Wave 4 (if need ed)	
Study Months					
Wave 1: Seeds randomized (1:1) to attend GE or IA condition  Workshop (WS)	16				
Wave 2: Recruitees who participate attend WSs		28 14			
WS Attendees who become PHAs					
Wave 3: Recruitees who participate attend WSs			28 14		
WS attendees who become PHAs					
Wave 4: Recruitees who participate attend WSs				28	
WS Attendees who become PHAs					
Total Attendees/wave (N= 98 <del>100</del> )	16	28	28	28 <del>30</del>	
Follow-up interviews		16	28	28	28

[figure not shown]

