online intervention materials as soon as they have completed the pre-intervention assessment. These include a link for the PrEP information/motivational video that also is part of the GE workshop, and links for a SA government-sponsored PrEP information website and a government-sponsored contraceptive information website. These materials constitute what would ordinarily be available to women receiving information about PrEP in a clinic or by themselves on the web. Women will be able to access and review these materials whenever they want. Additionally, participants will be sent the IPV component described above, and will be given instruction for women who want to be PHAs, as described above.

Quality Control. All GE intervention sessions will be audio-recorded, with the recording serving as the basis for weekly supervision. Facilitators' reports, completed following each session, will indicate problems, unusual circumstances and difficult issues.

Post intervention activities (both conditions). Brief post-assessments will be conducted. As part of the post-assessment, women will be asked if they want to speak with the study nurse about PrEP and/or about anything else. Notifications will be sent to staff when anyone responds "yes"; the study nurse will be notified to make a counseling appointment with the woman. After the post-assessment, women who wish to become PHAs will be given recruitment coupons and literature. Contact information will be confirmed and appointments for 3-month follow-up assessments made.

PrEP clinical assessment. After completing the online intervention (either condition), women will be invited to undergo individual counseling to help them determine if they want to take up PrEP. The counseling will be conducted by the MRC-GHCU staff nurse (who is a trained HIV C&T counselor), either remotely using WhatsApp or at the MRC- GHCU Ridge Road Site, in a private space. If the participant wishes to take up PrEP, the nurse will conduct HIV counseling and testing (HCT). Counselling and, if chosen, HIV-testing (optional) will be conducted using the MRC Gender and Health Research Unit PrEP counselling and HIV-testing SOP. This SOP follows standard DOH guidelines and uses publicly available and approved HIV-self testing kits (OraQuick). If women wish to self-administer the HIV test from home, the nurse will be available for guidance in conducting the test and for counseling regarding the results.

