by the Gender and Health Research Unit of the Medical Research Council to counsel women around PrEP and conduct HIV counseling and testing, either in person at the MRC office or via a telehealth nurse visit. HIV testing will be done using Oraquick®, an MRC-approved HIV self-test kit, either at the MRC office or offsite by the woman herself, with guidance from the nurse. We therefore propose to revise the primary study outcome to the following: ***having an individual discussion with the study nurse about taking up PrEP (either in-person or via telehealth). Undergoing HIV self-testing guided by the study nurse (either in-person at the GHRU office or via telehealth visit) will be a secondary outcome, as will initiating PrEP if eligible for PrEP (HIV-negative).***

These outcomes will be measured as follows: On the post-test assessment, women will be asked if they wish to speak with the study nurse about PrEP (and/or about any other issues). A “yes” response will trigger a notification to project staff, who will inform the study nurse. The study nurse will then contact the individual participant to arrange the counseling session. The study outcome will be considered to have been enacted when the participant has a PrEP counseling session. This, along with the result of PrEP counseling (e.g., underwent HIV testing or not, PrEP-eligible or not, and will initiate PrEP or not), will be documented by the nurse.

The revised specific aims of this study are as follows:

1. **Formative Work (no changes):** To ***inform intervention development*** through
  - a. Focus groups (six) with at-risk AGYW aged 18-25, grouped by age and recruitment venue (community, family planning clinic) to explore knowledge of, beliefs about, motivators for, and concerns about PrEP in the context of gendered relationship dynamics and PrEP-related stigma;
  - b. Qualitative interviews with men (10 known HIV-positive and 10 HIV-negative or of unknown status) who have female partners aged 18-25 to understand men’s views of PrEP and of their partners’ use of PrEP.
2. **Intervention development (revised):** In collaboration with an Intervention Development Working Group (IDWG) of AGYW, to ***develop a virtual group-based Gender-Enhanced PrEP Information-Motivational workshop***, drawing on our formative Aim 1 data and strategies from our prior HIV prevention interventions, ***and to choose a PrEP video and a PrEP informational website for the individual digital access control condition.***

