## Data Analysis

Workshops: Compare women randomized to the virtual group-interactive workshop with those randomized to individually-accessed links to a PrEP promotional video and PrEP information on the **primary outcome of having an individual discussion with the study nurse about the possibility of taking up PrEP; undergoing HIV self-testing guided by the study nurse (either in-person at the GHRU office or via telehealth visit) (secondary outcome); if eligible for PrEP, initiating PrEP (secondary outcome)**, and, for all women, changes in hypothesized mediators (information, risk perception, gender barriers, outcome beliefs, PrEP-stigma, peer norms) post-intervention and at 3-month follow-up.)

To compare the **primary and secondary outcomes** across the two workshop conditions, we will use generalized linear models (GLM) with a logit link function and the method of generalized estimating equations (GEE) to account for the effect of clustering within recruitment chain. The logit link function is appropriate because the primary and secondary outcomes are dichotomous and characterized as yes/no if achieved at any time over the course of the study by the time of the 3-month follow-up interview. Intervention condition (Gender-Enhanced or Individual Access) is the primary predictor. Although the original data analysis plan also specified accounting for clustering by workshop group attended, we will not account for clustering by workshop group because women in the IA condition received the intervention as individuals rather than as groups.

We will adjust for any substantial baseline differences by condition on age. We will also adjust for any substantial differences by other demographic and behavioral characteristics, such as education level, whether attending school, has a primary partner, sexual risk behaviors (to be defined), relationship power, reported intimate partner violence if these factors differ substantially by condition at baseline and are also associated with the outcome (i.e., meet the conditions of confounding).

To assess if being a PHA, i.e., talking to other women about HIV prevention serves as an additional intervention dose, a secondary analysis will include a variable for whether the woman served as a PHA and recruited other workshop attendees (yes/no).

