As a second step, we want to know whether, apart from the intervention, any of the hypothesized mediators are associated with the outcomes, e.g., whether women who at pre-test have low PrEP stigma, high perceived risk, low gender barriers for example, were more likely to have a nurse conversation, undergo HIV testing, initiate PrEP. These analyses will be conducted adjusting for intervention condition.

Finally, any mediators that are altered by the intervention will be included in the earlier models testing intervention effects of gender-enhanced intervention on primary study outcomes. A substantial reduction in the estimate of effect for the gender-enhanced intervention once the mediator is included in the model gives evidence that the hypothesized mediator explains in part the effect, i.e., that the intervention worked, for example, by reducing PrEP stigma or increasing risk for HIV.

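### The final mediation step does not require the models with and without the mediator to use the same women, so the change in the GE coefficient can mix mediation with a changed sample

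*SAP*

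**What the plan says.** In the SAP, Data Analysis, the mediator analysis has three steps. The last one says that "any mediators that are altered by the intervention will be included in the earlier models testing intervention effects of gender-enhanced intervention on primary study outcomes". The decision rule follows: "A substantial reduction in the estimate of effect for the gender-enhanced intervention once the mediator is included in the model gives evidence" that the mediator explains part of the effect. The SAP does not say which score enters the model (post-test or 3-month), how missing scores are handled, or whether the two fits share a sample.

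The earlier models take the nurse discussion, HIV self-testing and PrEP initiation as binary outcomes, "characterized as yes/no if achieved at any time over the course of the study by the time of the 3-month follow-up interview". The SAP's December 2020 revisions say the nurse documents the counselling session and its result. The protocol's account of study outcomes (Assessment Instruments) gives the nurse and the 3-month survey as sources.

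The usual route to the nurse runs through a survey. The SAP states: "On the post-test assessment, women will be asked if they wish to speak with the study nurse about PrEP". A yes "response will trigger a notification to project staff, who will inform the study nurse". The protocol agrees: "As part of the post-assessment, women will be asked if they want to speak with the study nurse". Under its PrEP clinical assessment heading, the protocol also invites women to counselling after the online intervention and lets those who decline speak with the nurse later.

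On loss, the protocol's recruitment section sets a target of 98 to 100 women completing and adds that "we anticipate that we may need to enroll up to 120 women".

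**The concern.** Comparing a coefficient before and after adding a covariate is informative about that covariate only if both fits use the same women. Here the outcome and the mediator come from different sources. A woman with no later survey can still be scored on the nurse outcome, but she has no post-intervention mediator score. Standard GLM and GEE software drops her as soon as the score enters the model.

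For a missing post-test, that exclusion is linked to the outcome. Without a post-test a woman lacks the usual trigger for the nurse contact. She tends to count as 'no' in the first model and is absent from the second.

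At stake is the explanatory claim that the workshop worked by, for example, reducing stigma. That reading could depend partly on who skipped a survey in each arm. The primary and secondary comparisons themselves are not affected.

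**Working it through.** The plan states no figure for this step, so there is none to reproduce. The check asks how far the GE coefficient moves when unscored women are dropped and the mediator explains nothing.

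**Inputs**
- Enrolled: 120, the protocol's upper figure, taken as 60 per arm (assumed).
- Unscored: 20, i.e. 120 minus 100 completers. That these women lack the score is an assumption, and so is every arm split.
- Unscored women counted as 'no' (assumed; relaxed below).
- Outcome rates among scored women, GE v IA, built from the SAP's Power Considerations:
  - 53% v 20%: the lowest control rate plus 33 points.
  - 85% v 50%: the SAP's illustrative pair.
  - 65% v 50%: 50% plus the 15-point minimally relevant gain.

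**Formula.** With d unscored in an arm and rate p among the scored, the all-women rate is (60 − d) × p / 60. Compare the log odds ratio (log OR) in all 120 women with that in scored women only.

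**Example, 85% v 50%, loss 10/10**
- All women: GE 50 × 0.85 = 42.5 of 60, odds 42.5/17.5 = 2.43. IA 50 × 0.50 = 25 of 60, odds 25/35 = 0.714. OR 3.40, log OR 1.22.
- Scored women: OR (0.85/0.15)/(0.50/0.50) = 5.67, log OR 1.73.
- Change: +42%.

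**Results: log OR in all women → in scored women**

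| Loss GE/IA | 53% v 20% | 85% v 50% | 65% v 50% |
|---|---|---|---|
| 10/10 | 1.38 → 1.51 (+10%) | 1.22 → 1.73 (+42%) | 0.50 → 0.62 (+23%) |
| 5/15 | 1.68 → 1.51 (-10%) | 1.77 → 1.73 (-2%) | 0.90 → 0.62 (-31%) |

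Loss of 15/5 raises the coefficient further: +40% at 53% v 20%, and +137% at 85% v 50%.

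**If 20% of unscored women still reach the nurse.** Add 0.2 × d events to each arm.
- 85% v 50%, loss 10/10: GE 44.5/15.5, IA 27/33, log OR 1.26, change +38%.
- 65% v 50%, loss 5/15: GE 36.75/23.25, IA 25.5/34.5, log OR 0.76, change -19%.
- 85% v 50%, loss 5/15: GE 47.75/12.25, IA 25.5/34.5, log OR 1.66, change +4%.
- 53% v 20%, loss 5/15: GE 30.15/29.85, IA 12/48, log OR 1.40, change +8%.

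**With smaller loss.** Three unscored per arm, all 'no', gives about +3% at 53% v 20% and +13% at 85% v 50%.

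**Same-women check.** About 1,500 simulated trials per case used a mediator that GE shifts but that has no effect on the outcome (logistic model, no recruitment-chain clustering). Mean GE log OR:

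| Case | All women | Scored, no mediator | Scored, with mediator |
|---|---|---|---|
| 53% v 20%, 10/10 | 1.41 | 1.55 | 1.57 |
| 53% v 20%, 5/15 | 1.72 | 1.55 | 1.57 |
| 65% v 50%, 5/15 | 0.91 | 0.63 | 0.63 |

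Nearly all of the movement comes from the change of sample. On the same women it is about 1% or less.

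**Missing only the 3-month survey.** Such a woman was asked the nurse question at post-test, and the nurse's record supplies her outcome. If her group's outcome rate equals that of retained women in the same arm, the expected shift is zero.

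**The case against.** The strongest reply is that the SAP does not prescribe a comparison of two samples. Data Analysis refers to women randomised but defines no analysis set. The protocol frames the pilot around women who finish the intervention and the assessments, and 120 is only a possible ceiling. If the analysed women are post-test completers and the post-test score is used, nobody drops out between fits. Most of the R250 payment is held until the post-test is done, so 20 missing post-tests is a high figure. The 85% v 50% pair is a supposition for sizing a later trial, with an outcome and comparator that have since been replaced. The step is exploratory, in a pilot aimed at feasibility. All of this stands. It limits the size and certainty of the problem, but it does not supply the missing same-women condition.

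A reader might infer three stronger things that the documents do not support:
- **That women lacking either later score mostly cannot have the nurse outcome.** This does not follow for women who miss only the 3-month survey. Even without a post-test, the protocol invites women to counselling and allows later contact.
- **That the rule will tend to manufacture mediation.** A false reduction needs loss concentrated in IA. GE is the more demanding arm, with assignments and a scheduled 90-minute group, so GE-heavy loss is at least as plausible. Equal or GE-heavy loss raises the coefficient in these scenarios and hides mediation.
- **That the percentages above estimate what will happen in this trial.** They are illustrations on assumed losses.

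**Conclusion.** The concern holds in a conditional form. As written, the rule lets the mediator model and its reference model use different women, and the change in coefficient is then not attributable to the mediator alone. With 20 of 120 women unscored and counted as 'no', and zero mediation, equal loss shifts the GE log OR by +10% to +42%, and a 5/15 GE/IA loss shifts it by -2% to -31%. The negative shifts are fragile: if 20% of unscored women reach the nurse, only the 65% v 50% case still falls (-19%). With few missing scores the shift is small, and with none it is absent. This bears on an exploratory step only, but the correction is simple enough that it should be made.

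**What to change.** In the final mediation step of the SAP's Data Analysis, state for each mediator:
- which time point's score enters the model;
- that the intervention-only model is refitted on exactly the women and covariates in the model containing that mediator;
- that mediation is judged only on the change between those two fits;
- that the number of women excluded is reported by arm, with their outcome rate.

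Multiple imputation of the mediator, from arm, pre-test score and outcome, is an optional sensitivity analysis.

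The cost is one or two sentences and one extra model fit per mediator, with no new data. The reference effect in the mediation table may differ from the headline estimate, which needs a footnote. The refit removes only the change of sample. It does not settle other questions about comparing coefficients on the logit scale.

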#### **Effect measure modifiers.** (updated with definitions on Dec 19 2022)

We will also want to evaluate whether the intervention was more (or less) effective among any particular sub-groups of women. Although these effect measure modifiers were not specified in the proposal, we included some in our pre-test measures (see measures document). I propose we examine the following:

1. Women with elevated depressive symptoms – using cutpoint of 10 on the CESD-10  
**If Depress10 = 1.** (however, n is only 27 so may not be possible)
2. Women reporting intimate partner violence themselves or whose social network includes women who experience IPV.  
**If networkAbuse =1 or IfIPV = 1.** (n = 57)
3. Women whose network includes those who engage in transactional sex  
**If O\_1 = 1 or O\_1 = 2.** (n = 45)
4. Women with higher (or lower) sexual relationship power  
**If relatcontrol3 = 1.** (however, N is only 28 in this group so may not be possible)
5. Women who have a primary male partner  
**IfMalePartner = 1.** (N = 85)
6. Women with higher levels of sexual risk.  
**IfSexRisk1 = 1.** (n = 64)
